5.4.2. Additional considerations

The definition of frequent race is any race (cDISC categories) with at least 40 subjects overall. The 'Other races' subgroup will include all races that do not meet this criterion.

6. ANALYSIS INTERPRETATION

All analyses are descriptive.

7. CONDUCT OF ANALYSES

7.1. Sequence of analyses

The final study report will contain the final analyses of all endpoints.

8. CHANGES FROM PLANNED ANALYSES

Not applicable

CONFIDENTIAL208236 (ROTA-096)
Statistical Analysis Plan Amendment 1

9. NON-STANDARD DATA DERIVATION RULES

The following sections describe additional derivation rules which are not presented in section 10.1 ([Business rules for standard data derivations and statistical methods](#)).

9.1. Data derivation

In all summaries of vaccine exposure the following will apply.

Co-administered vaccines will be those given on the same day as the study vaccine (HRV). Concomitant vaccinations will be all vaccines given on any other days.

9.2. Counting rules for occurrence of unsolicited adverse events

Following CBER request to comply with the CDISC Vaccines Therapeutic Area guide, the SDTM have been updated on October 2020. One of the updates requires that solicited events which continue beyond the observation period be stored in the Adverse Events (AE) domain. These solicited events will not be included in the summaries of unsolicited adverse events.

CONFIDENTIAL208236 (ROTA-096)
Statistical Analysis Plan Amendment 1

10. ANNEXES

10.1. Business rules for standard data derivations and statistical methods

This section contains GSK Vaccines' standard rules for data display and derivation for clinical and epidemiological studies. These rules will be applied along with those detailed in section 9 (additional study-specific rules).

10.1.1. Attributing events to vaccine doses

The dose relative to an event is the most recent study dose given to a subject prior to the start of a given event. For example, if the start date of an AE is between Dose 1 and Dose 2, the relative dose will be Dose 1.

If an event starts on the same day as a study dose, the relative dose will be derived from the additional information provided in the eCRF using the contents of the flag indicating if the event occurred before or after vaccination. If 'after vaccination' is selected, the relative dose for the event will be the one administered on the start day of the event. If 'before vaccination' is selected, the relative dose for the event will be the dose prior to this one.

10.1.2. Handling of missing data

10.1.2.1. Dates

When partially completed dates (i.e. with missing day or month) are used in calculations, the following standard rules will be applied:

- A missing day will be replaced by 15
- A missing day and month will be replaced by June 30th.

The following exceptions apply:

- Adverse event start dates with missing day:
 - If the event starts in the same month as at least 1 of the study doses, the contents of AE.AESTRTPT (the flag indicating if the event occurred before or after vaccination) will be used to complete the date. If 'after vaccination' is selected, the imputed start date will match the first (or only) study dose given during that month. If 'before vaccination' is selected, the imputed date will be 1 day before the first (or only) study dose given during that month.
- Adverse event start dates with missing day and month:
 - If the event starts in the same year as at least 1 of the study doses, the contents of AE.AESTRTPT (the flag indicating if the event occurred before or after vaccination) will be used to complete the date. If 'after vaccination' is selected, the imputed start date will match the first (or only) study dose given during that

CONFIDENTIAL

208236 (ROTA-096)
Statistical Analysis Plan Amendment 1

year. If 'before vaccination' is selected, the imputed date will be 1 day before the first (or only) study dose given during that year.

All other cases of incomplete AE or concomitant medication/vaccination start date will follow the standard rules above.

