Type of contact	Visit 1	Visit 2	Visit 3*/*	ESFU	Refer to Section 8.4 for study procedures to be considered during special circumstances (Amended 30 March 2020)
Timepoints	Day 1	Month 1-2	Month 2-4	Month 7-8	
Vaccine replacement dose administration in case of regurgitation/vomiting	●	●			If regurgitation or vomiting, which may have impaired vaccine take, occurs within 30 minutes after vaccination, a single replacement dose may be given at the same vaccination visit at the discretion of the investigator. This information should be recorded in the eCRF. The subject should continue to participate in the study.
Safety assessments					
Record any concomitant medications/vaccinations	●	●	●		Concomitant administration of routine pediatric vaccines will be allowed according to the local immunization practices in each participating country. All concomitant vaccinations given during the study period will be recorded in the eCRF (See Section 7.5 for more information)
Distribution of diary cards	0	0			
Recording of solicited AEs within 8 days after each vaccination (Day 1-Day 8) by subjects' parent(s)/LAR(s) in diary card	●	●			(See Section 12.3.6 for more information)
Recording of non-serious unsolicited AEs within 31 days after each vaccination (Day 1-Day 31) by subjects' parent(s)/LAR(s) in diary card.	●	●			(See Section 12.3.6 for more information)
Return of diary cards		0	0		
Diary card transcription by the investigator or designee		●	●		
Recording of AEs/SAEs leading to withdrawal from study	●	●	●	●	
Recording of SAEs	●	●	●	●	(See Section 12.3.6 for more information)
Recording of SAEs related to study participation, or to a concurrent GSK medication/vaccine	●	●	●	●	(See Section 12.3.6 for more information)
Safety contact				●	A safety follow-up contact will be done by a telephone call or any other convenient procedure to collect information on SAEs and medication taken for treatment of SAEs.
Study conclusion				●	(See Section 5.4 for more information)

ESFU=Extended safety follow-up; AE=Adverse event; SAE=Serious adverse event; LAR=Legally acceptable representative; eCRF=electronic case report form

- is used to indicate a study procedure that requires documentation in the individual eCRF
- is used to indicate a study procedure that does not require documentation in the individual eCRF

CONFIDENTIAL

208236 (ROTA-096)
Protocol Amendment 2

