12.3.6. Detecting and recording adverse events and serious adverse events

A paper diary, hereafter referred to as subject diary will be used in this study to capture solicited and unsolicited AEs. The subject's parent(s)/LAR(s) should be trained on how and when to complete each field of the subject diary.

The subjects' parent(s)/LAR(s) will be instructed to contact the investigator immediately should the subjects manifest any signs or symptoms they perceive as serious.

Subject diary training should be directed at the individual(s) who will perform the measurements of AEs and who will enter the information into the subject diary. This individual may not be the subject's parent(s)/LAR(s), but if a person other than the subject's parent(s)/LAR(s) enters information into the subject diary, this person's identity must be documented in the subject diary/subject's source record. Any individual that makes entries into the subject diary must receive training on completion of the subject diary at the time of the visit when subject diary is dispensed. This training must be documented in the subject's source record.

At each vaccination visit, subject diaries will be provided to the subject's parent(s)/LAR(s). The subject's parent(s)/LAR(s) will be instructed to measure and record the oral or axillary or rectal body temperature, and any solicited general AEs (i.e. on the day of vaccination and during the next 7 days) or any unsolicited AEs (i.e. on the day of vaccination and during the next 30 days) occurring after vaccination. The subject's parent(s)/LAR(s) will be instructed to return the completed subject diaries to the investigator at the next study visit.

CONFIDENTIAL208236 (ROTA-096)
Protocol Amendment 2

- Collect and verify completed subject diaries during discussion with the subject's parent(s)/LAR(s) on Visit 2 and Visit 3.
- Any unreturned subject diaries will be sought from the subject's parent(s)/LAR(s) through telephone call(s) or any other convenient procedure.

The investigator will transcribe the collected information into the eCRF in English.

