12.3.6.1. Time period for detecting and recording adverse events and serious adverse events

All AEs within 31 days following administration of each dose of study vaccines (Day 1 to Day 31) must be recorded onto the appropriate section of the eCRF, irrespective of intensity or whether or not they are considered vaccination-related.

The time period for collecting and recording SAEs will begin at the first receipt of study vaccines and will end 6 months following administration of the last dose of study vaccines for each subject. See Section [12.3.7](#) for instructions on reporting of SAEs.

All AEs/SAEs leading to withdrawal from the study will be collected and recorded from the time of the first receipt of study vaccine.

In addition to the above-mentioned reporting requirements and in order to fulfill international reporting obligations, SAEs that are related to study participation (i.e. protocol-mandated procedures, invasive tests, a change from existing therapy) or are related to a concurrent GSK medication/vaccine will be collected and recorded from the time the subject's parent(s)/LAR(s) consents to participate in the study until she/he is discharged from the study.

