10.1.3.6. Onset day

The onset day for an event (e.g. AE, medication, vaccination) is the number of days between the last study vaccination and the start date of the event. This is 1 for an event occurring on the same day as a vaccination (and reported as starting after vaccination).

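### For a last dose given in about the first half of a month, dating a non-serious AE with a missing day to the 15th can move it past Day 31 and out of the primary unsolicited AE table

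*SAP*

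**What the plan says.** SAP Amendment 1, section 10.1.2.1, applies "When partially completed dates (i.e. with missing day or month) are used in calculations". The general default is "A missing day will be replaced by 15"; if the month is missing too, the date becomes 30 June. For AE start dates there is an exception based on the before/after-vaccination flag, but it applies only "If the event starts in the same month as at least 1 of the study doses", or in the same year when the month is also missing. Everything else goes back to the default: "All other cases of incomplete AE or concomitant medication/vaccination start date will follow the standard rules above". The first SAP version has the same rules.

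SAP 10.1.3.6 counts the onset day from the last study dose: "This is 1 for an event occurring on the same day as a vaccination". SAP 5.4.1 tabulates the percentage of subjects with unsolicited AEs in the Day 1–31 window. No section limits the imputed date to that window or keeps an event because of the period for which it was collected.

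On collection, Protocol 12.3.6.1 states: "All AEs within 31 days following administration of each dose of study vaccines (Day 1 to Day 31) must be recorded". The Schedule of Activities agrees ("Recording of non-serious unsolicited AEs within 31 days after each vaccination"), and Protocol 12.3.6 has parents record "any unsolicited AEs (i.e. on the day of vaccination and during the next 30 days".

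**The concern.** A non-serious AE is normally in the database because it began by Day 31. If its start day is missing, that fact still tells us something about the date. The default ignores it and can assign a date that contradicts the reason for collection. Whether the event is counted then depends on the calendar day of the dose, not on anything about the event.

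The SAP's other missing-data rules lean towards inclusion. An event in a dose month flagged as after vaccination is dated to the dose day (10.1.2.1), and missing daily recordings of a solicited AE marked as present still count in the Any row (10.1.2.2). The default for the following month works the other way. All analyses are descriptive within-group percentages, so any loss shows directly as a lower reported rate.

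**Working it through.** The plan gives no figure for this point, so the check is date arithmetic.

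**Inputs from the documents**
- Default date: the 15th of the recorded month, if no dose was given in that month (SAP 10.1.2.1).
- Onset day = (imputed start date − dose date) + 1 (SAP 10.1.3.6).
- Window: dose date to dose date + 30 days, i.e. Day 1–31 (Protocol 12.3.6).
- Dose interval: 28–83 days (Protocol Table 2; SAP 5.1, code 2080).

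**Assumptions, not in the documents**
- Dose dates spread evenly over 2019–2020.
- Onset either uniform over Day 1–31 or declining as exp(−k/τ), where k is days since the dose.

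**Step 1: cut-off.** For a dose on day d of a month with L days, the 15th of the next month is Day L − d + 16. This exceeds 31 when d ≤ L − 16: the 15th of a 31-day month, the 14th of a 30-day month, the 12th of a 28-day month.

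**Step 2: examples, each for a last dose, AE recorded as April.**

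| Last dose | Window ends | 15 April is | Counted? |
|---|---|---|---|
| 5 March | 4 April | Day 31 − 5 + 16 = 42 | No |
| 15 March | 14 April | Day 32 | No |
| 16 March | 15 April | Day 31 | Yes |
| 20 March | 19 April | Day 27 | Yes |

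For the year rule, take a last dose on 20 December 2019, with a window to 19 January 2020. A January AE dated only 2020 goes to 30 June 2020. That is 11 days to year end plus 182 days = 193 days later, or Day 194.

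**Step 3: how often, no later dose in the AE's month, uniform onset.**
- Dose-date and onset-day pairs: 731 × 31 = 22,661.
- Pairs with onset in a later calendar month than the dose (default applies): 11,156.
- Imputed to Day 32 or later: 2,520.
- Share of default-rule cases: 2,520 / 11,156 = 22.6%. Share of all missing-day cases: 2,520 / 22,661 = 11.1%.
- Of the 2,520, doses on or before the 15th account for 2,516. The other 4 follow doses at the very end of January, whose window reaches March.

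**Step 4: early-peaking onset, same setting.**

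| τ (days) | Share of default-rule cases moved out | Share of all missing-day cases |
|---|---|---|
| 5 | 3.3% | 0.5% |
| 10 | 10.6% | 2.8% |
| 20 | 16.4% | 6.0% |

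**Step 5: Dose 1.** If 5 March is Dose 1, a Dose 2 given 28–56 days later falls on 2–30 April. April then contains a dose and the exception replaces the default. Enumerating the intervals with uniform onset:
- 28 to 44 days: none moved out by the default.
- 45 days: the first losses, 14 of 8,096.
- 56 days: 2,221 of 10,857 (20.5%).
- 61 to 83 days: 2,520 of 11,156 (22.6%), as for a last dose.

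If both doses contribute equally, a 35-day schedule gives (0 + 2,520) / (22,661 + 22,661) = 5.6% of all missing-day cases, and a schedule of 61 days or more gives 11.1%. With τ = 10 these become 2.8% / 2 = 1.4%, and 2.8%.

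**Step 6: the alternative date.** Using the 1st of the AE's month leaves 0 of 11,156 default-rule cases outside the window. This must be so: a window that runs into a later month contains the 1st of that month. An AE in a month the window does not reach stays out. After a 5 March dose, for example, an AE recorded as May is dated 1 May, which is Day 58.

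**The case against.** The midpoint default is a declared sponsor standard and a common convention, and earliest-date imputation trades under-counting for over-counting. Onset days should seldom be missing, because parents keep a diary that the site verifies with them (Protocol 12.3.6).

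Nor does being recorded always prove onset in the window. Visit 3 may be up to 83 days after Dose 2 (Protocol Table 2), and parents are asked about changes since vaccination or the last visit (Protocol 12.3.6.2.1). SAEs and AEs leading to withdrawal are collected beyond Day 31 (Protocol 12.3.6.1), and SAEs enter the unsolicited summaries (SAP 10.1.2.3).

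Most of this stands as a limit on scope and size. It does not rescue the rule where the rule fails: after a last dose on 5 March, no in-window April date is near the 15th. Partial dates are also plausible. Events that are neither medically attended nor a worry to the parents are gathered by interview at the next visit (Protocol 12.3.4), and under special circumstances diary cards may come back as late as study end (Protocol 8.4).

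A reader might infer three stronger things that the documents do not support.
- That every AE in a month without a dose is lost. With uniform onset about 77% of default-rule cases stay inside (100% − 22.6%), and Dose 1 events on a 1-month schedule do not reach the default's failing range.
- That 22.6% of unsolicited AEs disappear. The denominator is AEs with a missing day in a later month than the dose, under one onset assumption.
- That the comparison of the two groups is biased. The same rule applies to both randomized groups, and nothing in it favours one of them.

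**Conclusion.** The point holds in a narrow form. For a last dose, or for Dose 1 with an interval above about 6 weeks, given on or before the Step 1 cut-off day, the default dates a non-serious AE collected under the Day 1–31 rule to Day 32 or later. It then drops out of the primary unsolicited AE table. For Dose 1 at 28–42 days the default does no such harm, because Dose 2 falls in the AE's month and the exception applies. How the exception itself dates those events is a separate matter, not assessed here.

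The conditional shares rest on assumed dose dates and onset patterns. The absolute effect cannot be calculated, because the documents do not give the frequency of partial dates. A subject leaves a table row only if no other counted event keeps them in it. The effect on reported rates is therefore probably small. It is worth correcting as an avoidable undercount in a primary safety table, but it does not threaten the trial's conclusions.

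**What to change.** Add one sentence to SAP 10.1.2.1. For non-serious AEs that did not lead to withdrawal, if the start date is partial and no study dose was given in the known month (or year), impute the earliest date that agrees with the known part and is not before the most recent dose. In practice this is the 1st of the month, or 1 January.

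Keep the 15th and 30 June for SAEs, AEs leading to withdrawal and dates other than AE start dates. List all imputed AE dates by group, so that readers can see how many counts depend on imputation.

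The cost is that sentence, a small programming change and one listing. The downside is that a few non-serious AEs recorded at a late visit that truly began after Day 31 may be counted inside the window.

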12.3.1.3. Events NOT meeting the adverse event definition

- Situations where an untoward medical occurrence did not occur (e.g. social and/or convenience admission to a hospital, admission for routine examination).
- Anticipated day-to-day fluctuations of pre-existing disease(s) or condition(s) present or detected at the start of the study that do not worsen.
- Pre-existing conditions or signs and/or symptoms present in a subject prior to the first study vaccination. These events will be recorded in the medical history section of the eCRF.

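### SAP 10.1.2.1 does not say which dose the before/after flag refers to, so a partially dated AE between the doses can be imputed outside the Day 1-31 window

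*SAP*

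**What the plan says.** SAP 10.1.2.1 (Dates) treats partial AE start dates by means of "the flag indicating if the event occurred before or after vaccination".

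- **Day missing, flagged after:** "the imputed start date will match the first (or only) study dose given during that month".
- **Day missing, flagged before:** "the imputed date will be 1 day before the first (or only) study dose given during that month".
- **Day and month missing, flagged before:** "the imputed date will be 1 day before the first (or only) study dose given during that year".

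SAP 10.1.1 then gives the attribution rule: "The dose relative to an event is the most recent study dose given to a subject prior to the start of a given event". When an event starts on a dose day, the same kind of flag is read against that day's dose: "If 'before vaccination' is selected, the relative dose for the event will be the dose prior to this one".

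On what can be an AE at all, Protocol 12.3.1.3 excludes "Pre-existing conditions or signs and/or symptoms present in a subject prior to the first study vaccination"; these go to medical history. Protocol 12.3.6.1 makes one exception. SAEs related to study participation or to a concurrent GSK product are collected from consent, so they can precede Dose 1. The same section requires that "All AEs within 31 days following administration of each dose of study vaccines (Day 1 to Day 31) must be recorded". Protocol Table 2 allows 28 to 83 days between the doses.

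**The concern.** Conditions present before Dose 1 are not AEs, apart from the consent-period SAEs. So an AE record flagged as starting before vaccination will, in most cases, concern an event between Dose 1 and Dose 2. Yet the rule counts back from the first dose in the month or year. If both doses are in that period, the event is placed before Dose 1, where SAP 10.1.1 has no dose to attach it to.

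If only Dose 2 is in the month, the event keeps Dose 1 as its relative dose, but it receives the latest date that the record allows. With a long enough gap that date is past Day 31.

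Unsolicited AEs within 31 days are a primary endpoint, and SAP section 6 makes all analyses descriptive. The counts are therefore the result, and an imputation default should not remove an event that is known to follow vaccination.

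**Working it through.** The documents state no figure for this rule, so there is none to reproduce. The inputs are the rules above, the 28-83 day interval (Protocol Table 2), the Day 1-31 window (SAP 5.4.1) and 675 subjects per group (Protocol 10.1). Assumption: Dose 1 dates are spread evenly over the 365 days of 2019.

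**1. Both doses in the same month (day missing).** A gap of g days fits in a month of L days for L - g possible Dose 1 dates. 2019 has seven months of 31 days, four of 30 and one of 28.

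- g = 28: 7×3 + 4×2 = 29; 29/365 = 7.9%
- g = 29: 7×2 + 4×1 = 18; 18/365 = 4.9%
- g = 30: 7×1 = 7; 7/365 = 1.9%
- g = 31 or more: 0%

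Over all 56 allowed gaps: (29 + 18 + 7)/(365×56) = 54/20,440 = 0.26%.

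Example: doses on 1 and 30 October 2019, AE start October 2019, flagged before. The rule gives 30 September, which has no relative dose and is not counted. If the flag concerns Dose 2 and the date is anchored there, the start is 29 October, Day 29 after Dose 1, and the event is counted.

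**2. Both doses in the same year (day and month missing).** The share is (365 - g)/365.

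- g = 28: 337/365 = 92%
- g = 83: 282/365 = 77%

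This is how often the doses share a calendar year. It is not the proportion of AEs lost, because it matters only for a before-flagged AE with nothing but the year known.

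**3. Only Dose 2 in the AE month (day missing).** The imputed start is Dose 2 minus 1 day. With the dose day as Day 1, this is Day g, so every gap above 31 days puts the event outside the window.

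Example: Dose 1 on 10 October, Dose 2 on 14 November (g = 35). The rule gives 13 November, Day 35. The compatible dates are 1-13 November, Days 23-35, and 9 of these 13 are within Day 31.

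Over all Dose 1 dates, 353 of 365 leave at least one day in the month before Dose 2; in the other 12, Dose 2 falls on the first of the month. The average share of compatible dates inside Day 31 is:

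- g = 35: 305 of 353 infants have some date inside, on average 70% of their dates; 305/353 × 0.70 = 61%
- g = 42: 221 of 353 have some date inside, on average 43%; 221/353 × 0.43 = 27%
- g = 60: 0.1%
- g = 61 or more: none

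The cut-off follows directly. The earliest compatible date is at most 30 days before Dose 2, which is Day g + 1 - 30 = g - 29. This is within Day 31 only if g is 60 or less.

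**4. Effect of one subject.** 1/675 = 0.15 points. With Clopper-Pearson limits, 10/675 is 1.5% (0.7-2.7) and 9/675 is 1.3% (0.6-2.5); 100/675 is 14.8% (12.2-17.7) and 99/675 is 14.7% (12.1-17.6). The limits for 10 and 100 events agree with Protocol Table 10.

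**The case against.** The strongest reply is that SAP 10.1.2.1 never names the flag's reference dose. If, in a shared period, the flag refers to the first dose, an event between the doses is flagged after, is imputed to Dose 1 Day 1 and is counted. Nothing is lost. SAP 10.1.1 points the other way, but it governs events starting on a dose day. This stands: the loss in the shared period is conditional on how the flag is read.

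The reply does not clear the branch with only Dose 2 in the month. Read against Dose 2, which is also the dose the rule anchors on there, the result is Day g as shown. Read always against Dose 1, the event is flagged after and moves to Dose 2 Day 1, which is the wrong dose and falls inside the 8-day combined table.

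Reach is limited too. The shared month is nearly unreachable with a 28-day minimum. Year-only dates should be rare, since diary cards are verified with the parents at Visits 2 and 3. With gaps near two months, a date outside the window is nearly always right. The rule is a sponsor standard applied alike to both groups, and no hypothesis is tested. All of this limits the size; none of it supplies the missing definition.

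A reader might also infer that events flagged after vaccination always land on Dose 1 Day 1. They do so only when Dose 1 is in the period; if only Dose 2 is, they go to Dose 2 Day 1.

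**Conclusion.** The rule is incomplete, and it can take a reportable AE out of a primary safety count. In a shared month or year this depends on reading the flag dose by dose. In a month with only Dose 2 it affects gaps of 32-60 days, and mainly the shorter of these.

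The documents do not support the stronger conclusion that events between the doses are in fact being lost, or that 77-92% of any group of events is lost. They neither settle the flag's reference dose nor say how many AEs have partial dates. At about 0.15 points per affected subject, and with probably few such records, the likely effect is small. The percentages rest on evenly spread Dose 1 dates. This is worth correcting because the correction is cheap, not because it is likely to change the safety conclusions.

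**What to change.** In SAP 10.1.2.1:

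1. State which dose the flag refers to, in line with SAP 10.1.1, including when both doses share the month or year.
2. Never impute an AE start before Dose 1 unless the eCRF records that the event began before Dose 1.
3. For an AE that began before Dose 2, impute the earliest date compatible with the partial date and any end date, on or after Dose 1.
4. List events with imputed start dates separately.

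The cost is a few sentences and a small programming change. The downside is that a few events truly outside the 31-day window may be counted. Some truly outside the 8-day window may also enter the combined table, above all those with only the year known, for which the earliest compatible date is often Dose 1 Day 1. The listing in item 4 makes these visible.
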